8.0 STUDY OBJECTIVES

The objective of this study is to evaluate the efficacy, safety, and tolerability of levomilnacipran compared with placebo in pediatric outpatients (7-17 years) with MDD.

In addition, the study is designed to obtain pharmacokinetic (PK) data to define the PK profile of levomilnacipran in the pediatric population (7-17 years of age).

9.0 INVESTIGATIONAL PLAN

9.1 OVERALL STUDY DESIGN AND PLAN: DESCRIPTION

Study LVM-MD-14 will be a multicenter, randomized, double-blind, placebo- and active-controlled, flexible-dose, parallel group study in pediatric patients, ages 7-17 years. The study will be approximately 10 weeks in duration:

- 1-week screening/washout period
- 8-week double-blind treatment period
- 1-week double-blind down-taper period

The screening/washout period will be generally 1 week (\pm 3 days) prior to Visit 2 (Baseline), but may be extended up to a total of 5 weeks to accommodate prior medication washout or to repeat assessments. Patients will not receive any investigational product during the screening period.

Patients who meet the eligibility criteria at Visit 2 (Baseline) will be randomized to 1 of 3 treatment groups: placebo, levomilnacipran, or fluoxetine. See Section [9.4.5](#) for details regarding dose selection and timing.

All randomized patients who complete the 8-week double-blind treatment period and patients who prematurely discontinue from the study before completing 8 weeks of double-blind treatment should enter the 1-week, double-blind down-taper period unless it is considered not clinically appropriate by the Investigator.

All randomized patients must complete Visit 8/Early Termination (ET) Visit and, at the end of the down-taper period, return for Visit 9/Safety Follow-up (SFU) Visit. Patients who do not enter the down-taper period must return for Visit 9/SFU Visit approximately 1 week after Visit 8/ET Visit.

Approximately 480 patients (160 per treatment group) are planned to be randomized in the study.

[Figure 9-1](#) provides a schematic of the study design.

The coronavirus disease 2019 (COVID-19) pandemic developed after this study began, and this protocol has been amended to account for study procedures that may need to be modified in association with adhering to local guidelines or regulations or site flexibility to complete study-required procedures.

[figure not shown]
During the COVID-19 pandemic, remote study visits, in which data are collected via phone or videoconference, were and will continue to be possible when needed. To accommodate changes that sites may need to implement during the pandemic, Section 2.0 outlines the conduct of study assessments during on-site clinic visits, which is the preferred method of conducting the study, while study assessments for remote visits are included in Section 2.1. Sites will need to inform the Sponsor of the need for a remote visit in advance whenever possible.

In the event that it is required to perform procedures remotely, every effort should be made to perform the remote assessment in a manner as similar as possible to the on-site assessment. Patient data collected via phone or video conferencing should remain consistent with either method for each patient.

Detailed descriptions of each study visit are provided in Section 9.5.5.

Figure 9-1.

Study Design

Levomilnacipran treatment group: During the double-blind treatment period, patients will take levomilnacipran 10 mg/day on Days 1-3, 20 mg/day on Days 4-7, and 40 mg/day during Weeks 2 through 8. Based on therapeutic response and tolerability, an additional dose increase to 80 mg/day is permitted at Week 3. During the down-taper period, patients will take levomilnacipran 40 mg/day for 2 days, and then levomilnacipran 20 mg/day for 5 days.

Fluoxetine (active comparator) treatment group: During the double-blind treatment period, patients will take fluoxetine 10 mg/day on Days 1-7, and then 20 mg/day during Weeks 2 through Week 8. During the down-taper period, patients will take fluoxetine 10 mg/day for 7 days.

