9.4.2 Identity of Investigational Products

Investigational product will be supplied by AGN as capsules containing placebo or nontrade levomilnacipran 10 mg capsules, trade levomilnacipran 20 mg capsules, trade levomilnacipran 40 mg capsules, fluoxetine 10 mg capsules, or fluoxetine 20 mg capsules packaged in blister cards.

The blister cards will contain sufficient numbers of doses for the interval of days between scheduled visits plus additional doses to accommodate visit scheduling.

The blister cards will be labeled with the protocol number, storage information, warning language (viz, “Caution: New Drug—Limited by Federal Law to Investigational Use”), and instructions to take as directed. The Investigator will write the date, visit number, study week, and PID number on the label.

All investigational product will be provided and shipped to the study centers by AGN and must be stored in an appropriate secure area (eg, a locked cabinet in a locked room) at room temperature (25°C or 77°F, with a permitted range of 15°C-30°C or 59°F-86°F), and must be protected from light, heat, and moisture.

The Investigator is responsible for recording the receipt and use of all investigational product supplied and for ensuring the supervision of the storage and allocation of these supplies. All unused investigational product must be returned; and, whenever investigational product are returned, unit counts must be performed. All investigational product must be accounted for. At the end of the study, all unused investigational product and empty investigational product packages must be returned to the Sponsor at the address provided in the Study Reference Binder.

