9.4.5 Selection and Timing of Dose for Each Patient

All investigational products should be taken orally as a single dose, once-daily at the same time each day. After consent/assent is obtained, patients undergoing screening will be required to swallow a placebo capsule to confirm their ability to swallow the investigational product, as part of their eligibility assessment.

Patients who meet all eligibility criteria at Visit 1 (Screening) and who continue to meet all the eligibility criteria for participation in the study will be assigned a randomization number at Visit 2 (Baseline) and dispensed the corresponding blister card containing capsules of double-blind investigational product for Week 1. Patients will begin dosing with double-blind capsules on the next day. Patients will be instructed to take 2 capsules orally as a single dose, once daily at approximately the same time each day (morning dosing recommended), with or without food.

Dosing may be switched from the morning to another time of day if a patient prefers or if tolerability issues arise. However, any switch must allow at least 20 hours between 2 consecutive doses.

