9.4.5.2 Double-blind Treatment Period

The titration schedule is as follows:

- Levomilnacipran: Days 1-3, 10 mg/day; Days 4-7, 20 mg/day; Week 2 through Week 8, 40 mg/day; Based on therapeutic response and tolerability, an additional dose increase to 80 mg/day is permitted at Week 3.
- Fluoxetine 20 mg/day (active comparator): Week 1, 10 mg/day; Week 2 through Week 8, 20 mg/day

Patients will be assigned a randomization number at Visit 2 (Baseline) and dispensed the corresponding blister card containing capsules of double-blind investigational product for Week 1. Patients will begin dosing with double-blind capsules on the next morning. Patients will be instructed to take 2 capsules from each column (1 each from Row A and Row B) as a single dose daily each morning with or without food. The double-blind dosing regimen is presented in [Table 9-1](#).

Table 9-1.

Double-blind Dosing Regimen

Treatment Group	Row	Week					
		1		2	3-8	Down-Taper	
		Days 1-3	Days 4-7	Days 1-7	Days 1-7	Days 1-2	Days 3-7
Levomilnacipran 40 mg - 80 mg	A	LVM 10 mg	LVM 20 mg	LVM 40 mg	LVM 40 mg	LVM 40 mg	LVM 20 mg
	B	Placebo	Placebo	Placebo	Placebo	Placebo	Placebo
	A	Optional dose escalation to 80 mg as determined by treating physician			LVM 40 mg	LVM 40 mg	LVM 20 mg
	B				LVM 40 mg	Placebo	Placebo
Fluoxetine 20 mg	A	Fluoxetine 10 mg	Fluoxetine 10 mg	Fluoxetine 20 mg	Fluoxetine 20 mg	Fluoxetine 10 mg	Fluoxetine 10 mg
	B	Placebo	Placebo	Placebo	Placebo	Placebo	Placebo
Placebo	A	Placebo	Placebo	Placebo	Placebo	Placebo	Placebo
	B	Placebo	Placebo	Placebo	Placebo	Placebo	Placebo

ET = Early termination; LVM = levomilnacipran.

Patients will be instructed to return the blister card with any remaining investigational product, and to return it even if it is empty, preferably at the next study visit. Additional investigational product will be dispensed as per the schedule shown in Section 2.0.

If a patient experiences an AE, the investigational product may be stopped for up to a maximum of 4 consecutive days. The date and reason for missed doses must be recorded on the appropriate page of the eCRF. If appropriate, as deemed by the investigator, patient may resume medication at 40 mg/day or reduce to 40 mg/day (if taking 80 mg/day). Those unable to tolerate 40 mg/day should be discontinued from the study.

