9.4.5.3 Double-Blind Down-Taper Period

All randomized patients who complete the 8-week double-blind treatment period and patients who prematurely discontinue from the study before completing 8 weeks of double-blind treatment should enter the 1-week, double-blind down-taper period unless it is considered not clinically appropriate by the Investigator. The double-blind down-titration regimen is as follows:

- Levomilnacipran 40 mg/day and 80 mg/day: Days 1-2, 40 mg/day; Days 3-7, 20 mg/day
- Fluoxetine 20 mg/day: Days 1-7, 10 mg/day

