9.5.5 Schedule of Assessments

The schedule of study procedures and assessments is tabulated by visit in the [Schedule of Evaluations](#) in Section 2.0 and Section 2.1. The descriptions of the procedures to be performed at each visit are provided below.

The screening period should be 1 week (\pm 3 days) before Visit 2, but may be extended up to a total of 5 weeks to accommodate prior medication washout or to repeat assessments. The reason for the extended screening will be recorded in the source documents.

If necessary, visits may be conducted up to 3 days before or after the indicated postbaseline weeks relative to Visit 2 (Baseline).

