9.5.5.3 Visit 3 (End of Week 1)

At this visit, the following procedures will be performed:

- Review and record AEs
- Review concomitant medications
- Measure vital signs
- Complete efficacy evaluations
 - Administer CDRS-R (caregiver and patient)
 - Administer CGI-S
 - Administer CGI-I
- Administer C-SSRS (Since-Last-Visit). Results should be evaluated by the Investigator or designee before the patient leaves the study center
- Confirm investigational product return and assess investigational product compliance
- Dispense double-blind investigational product for the next visit per IWRS assignment and provide written and verbal instructions for dosing to patient and caregiver. Document that instructions were given in source documents
- If Visit 3 is done remotely, the study drug may be sent to patients via preferred courier or via curbside pickup must be approved in advance by the Sponsor
- Schedule next visits
 - Visit 4: 2 weeks (\pm 3 days) after Visit 2 and
 - Visit 5: 3 weeks (\pm 3 days) after Visit 2

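### The only levomilnacipran down-taper starts at 40 mg/day, so a child who stops in Week 1 on 20 (or, rarely, 10) mg/day has the dose raised on leaving unless the Investigator waives the taper

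*Protocol*

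**What the plan says.** - **Titration** (Protocol Section 9.4.5.2): "Levomilnacipran: Days 1-3, 10 mg/day; Days 4-7, 20 mg/day; Week 2 through Week 8, 40 mg/day", with an optional rise to 80 mg/day at Week 3.
- **Down-taper** (Protocol Section 9.1, text to Figure 9-1): "During the down-taper period, patients will take levomilnacipran 40 mg/day for 2 days, and then levomilnacipran 20 mg/day for 5 days". Table 9-1, SAP Section 4.0 and SAP Table 4-1 give the same regimen. Section 9.4.5.3 gives it under a dose label: "Levomilnacipran 40 mg/day and 80 mg/day: Days 1-2, 40 mg/day; Days 3-7, 20 mg/day". No other levomilnacipran taper appears in either document.
- **Who enters** (Protocol Sections 9.1 and 9.4.5.3): completers and early discontinuers alike "should enter the 1-week, double-blind down-taper period unless it is considered not clinically appropriate by the Investigator". No minimum exposure is set. Patients who do not enter the taper return for Visit 9/SFU about a week after Visit 8/ET.
- **Timing**: after Visit 2, "Patients will begin dosing with double-blind capsules on the next day" (Section 9.4.5). Visit 3 is due 1 week after Visit 2, within 3 days either way (Sections 9.5.5 and 9.5.5.2). At Visit 3 the site is to "Dispense double-blind investigational product for the next visit per IWRS assignment" (Section 9.5.5.3).
- **Supply**: cards hold doses for the interval between visits "plus additional doses to accommodate visit scheduling" (Section 9.4.2). Taper kits are assigned by IWRS at Visit 8/ET (Section 9.5.5.6).

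**The concern.** A down-taper should not exceed the dose the patient was taking. This one was built for patients at 40 or 80 mg/day, but the entry rule also sends in children who never reached 40 mg/day. For them the default raises the dose just as they leave, and some will be leaving because of an adverse event. Only the test arm is exposed, since the fluoxetine taper equals the Week 1 fluoxetine dose. What is at stake is the safety of 7 to 17 year olds, not the efficacy estimate.

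**Working it through.** No power or error-rate figure is involved. The check sets the scheduled dose on the last day of treatment (Section 9.4.5.2) against the taper (Sections 9.1 and 9.4.5.3, Table 9-1).

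**1. Size of the step**

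| Last dosing day | Levomilnacipran, last dose to first taper dose (mg/day) | Ratio | Taper days above last dose | Fluoxetine (mg/day) |
|---|---|---|---|---|
| Days 1-3 | 10 to 40 | 40/10 = 4 | 2 + 5 = 7 of 7 | 10 to 10 |
| Days 4-7 | 20 to 40 | 40/20 = 2 | 2 of 7 | 10 to 10 |
| Day 8 on, at 40 | 40 to 40 | 40/40 = 1 | 0 of 7 | 20 to 10 |
| Week 3 on, at 80 | 80 to 40 | 40/80 = 0.5 | 0 of 7 | 20 to 10 |

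The rise is confined to children who stop in Week 1. In total the taper supplies 2 × 40 + 5 × 20 = 180 mg. All of Week 1 supplies 3 × 10 + 4 × 20 = 110 mg, and Days 1-3 supply 30 mg.

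**2. Whether ordinary visit timing produces it**

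- Dosing Day 1 = Visit 2 + 1 day.
- Visit 3 = Visit 2 + 7 days, plus or minus 3, which is Visit 2 + 4 to + 10, or dosing Days 4 to 10. The nominal day is dosing Day 7, when the scheduled dose is 20 mg.
- The Week 2 supply at 40 mg/day is handed out only at Visit 3. A child who discontinues at or before that visit has not started it.
- For a late Visit 3 (Days 8-10) this assumes that the spare doses on the Week 1 card are at Week 1 strength, which Section 9.4.2 does not say. An on-time or early Visit 3 does not need that assumption.
- The 10-to-40 case requires dosing to stop on Days 1-3, before any scheduled post-baseline visit, so it should be rare.

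**3. How many children**

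The documents give no distribution of stopping days. Planned dropout is 17% (Protocol Section 9.7.9), so 0.17 × 160 = 27.2 levomilnacipran patients. The figures below are before any waiver.

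- Assumed share stopping in Week 1 of 0% to 25%: 27.2 × 0 = 0 to 27.2 × 0.25 = 6.8, or 0 to 7 children.
- Dropout even over 8 weeks: 27.2/8 = 3.4, of which 3.4 × 3/7 = 1.5 stop on Days 1-3 and 3.4 × 4/7 = 1.9 on Days 4-7.

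**The case against.** **The dose label.** Section 9.1 refers the reader to Section 9.4.5 for dosing. There, Section 9.4.5.3 labels the regimen as being for 40 and 80 mg/day, naming two levels where the arm is elsewhere written as a range. Read as the dose at stopping, this leaves a Week 1 stopper with no defined taper, not an instruction to step up. That reading is possible. Against it, the parallel fluoxetine label gives only 20 mg/day and reads as an arm name, and the text in Protocol Section 9.1 and SAP Section 4.0 carries no condition. On either reading these children are sent by default into a taper with no suitable dose.

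**The waiver.** The Investigator knows the study day, can read the schedule, and can waive the taper without unblinding. This is a real safeguard. But it is all-or-nothing, and nothing in the protocol warns that tapering a Week 1 stopper may raise the dose.

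**IWRS.** The IWRS Site User Guide (Section 9.4.3) is not among the documents, so kit logic may already prevent the step. This stands, and it is the first thing to check.

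**Limited harm.** The 20-to-40 step equals the planned Week 2 step and lasts 2 days. Section 9.4.5.2 also allows resumption at 40 mg/day after a short interruption for an adverse event. This stands as to size. However, those provisions are for children who continue treatment, and the same section says those who cannot tolerate 40 mg/day should be discontinued.

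**Late stage.** Section 9.7.8 reports an interim analysis after 62% of randomized patients had finished or discontinued. If the denominator is the planned 480 (an assumption), about 0.38 × 160 = 61 levomilnacipran patients remained, and even dropout gives 61 × 0.17/8, or about 1.3 children whom an amendment could still reach. The benefit is small, and so is the cost.

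**Conclusion.** The concern holds. As written, the default taper doubles the dose for a child stopping on Days 4-7, including at an on-time Visit 3, and quadruples it for the rare child stopping on Days 1-3. No lower-strength levomilnacipran taper is given anywhere. The number affected is probably small: 0 to 7 children under an assumed Week 1 share of 0% to 25% of dropouts, and about 3 with even dropout, before any waiver. The conclusion rests on reading the Section 9.4.5.3 label as an arm name and on IWRS not already blocking the step. Confidence is therefore moderate. It is a safety point worth correcting.

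**What to change.** First confirm what the IWRS assigns to a patient who terminates early in Week 1. Then state in Protocol Sections 9.1 and 9.4.5.3, Table 9-1, and SAP Section 4.0 and Table 4-1 that no taper dose exceeds the last dose taken, and programme IWRS to match.

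The simplest rule is that patients in any arm who stop on Days 1-7, or before starting the Week 2 card if Visit 3 is late, do not enter the down-taper and return for Visit 9/SFU about a week after Visit 8/ET. That route already exists (Sections 9.1 and 9.5.5.7), and applying it to every arm keeps the blind.

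The cost is a short protocol, SAP and IWRS amendment, with no new supply, visits or patients. The clinical price is no taper after at most about 7 days (up to 10 if Visit 3 is late) on 20 mg/day or less of levomilnacipran, or on 10 mg/day of fluoxetine.

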9.1.1 COVID-19 Specific Process

To promote patient safety and ensure the completion of study-required procedures during the COVID-19 pandemic, the following processes will be implemented.

The patient must not have signs/symptoms associated with COVID-19 infection or known exposure to a confirmed case of COVID-19 infection during 14 days prior to Screening. Patients who do not meet COVID-19 eligibility criteria must be screen failed and may only rescreen after they meet the following COVID-19 viral clearance criteria:

- Symptomatic patients: At least 2 negative viral tests in a row, ≥ 24 hours apart after at least 10 days have passed since recovery, defined as resolution of fever without use of antipyretics and improvement in respiratory symptoms (eg, cough, shortness of breath)
- Asymptomatic patients: At least 2 negative viral tests in a row, ≥ 24 hours apart after at least 10 days have passed since prior positive result (Note: patients who develop symptoms will follow guidance above for symptomatic patients)

Frequency or timing of COVID-19 testing and interval between testing for the above viral clearance criteria may be adjusted to account for epidemiological trends, updated information regarding infectivity and local/institutional guidelines.

Visit conduct options will allow remote visits as outlined below:

- Option 1: In-clinic visits

This is the preferred option. All study visits are performed as in clinic visits with all assessments outlined in the Schedule of Assessments in Section 2.0.

- Option 2: Remote visits (except screening)

This option is only to be used if local guidance, regulations, or the needs of the patient prevent the site or the patient from completing on-site visit procedures. Screening visits must take place as an in-clinic visit with all assessments outlined in the schedule of assessments in Section 2.0. All other visit procedures (V2-V8) can be completed remotely with the assessments outlined in Section 2.1. The study center needs to alert the Sponsor, ahead of time when possible, that a remote procedure was performed.

For remote visits, there is an option to have study drug delivered by preferred courier. Approval from the Sponsor study team must be obtained from the study center each time the preferred courier service is utilized.

9.2 DISCUSSION OF STUDY DESIGN, INCLUDING THE CHOICE OF CONTROL GROUPS

This placebo- and active-controlled, flexible-dose design with an 8-week double-blind treatment period was chosen based on prior studies that established the efficacy and safety of levomilnacipran in adult patients with MDD. In this study, Investigators must use a valid and reliable diagnostic method for recruiting and enrolling children and adolescents meeting *Diagnostic and Statistical Manual of Mental Disorders*, 5th Edition (DSM-5; [American Psychiatric Association 2013](#)) criteria for MDD.

A placebo arm is included for comparison since placebo-controlled superiority trials have been shown to be conducive to higher quality studies and to provide more reliable outcomes than non-inferiority comparisons to a previously approved drug ([Feifel 2008](#); [Laughren 2001](#); [Gispen-de Wied 2012](#)). In addition, placebo in place of the (limited) standard therapy should not cause irreversible health problems or extreme suffering (depression is recognized by the FDA as a condition in which there is substantial improvement and variability in placebo groups; see [FDA Guidance for Industry: E10, May 2001](#)).

Fluoxetine was selected as an active comparator for assay sensitivity in the present study because it is an SSRI approved by the FDA for the treatment of MDD in children and adolescents 8 years and older.

In the current study, safety and efficacy assessments are included in every visit to determine adequacy of response, safety, and tolerability for all patients.

9.3 SELECTION OF STUDY POPULATION

9.3.1 Inclusion Criteria

Patients must provide assent to participate and their parent/guardian/LAR and caregiver (even if the same as the parent/guardian/LAR) must provide written informed consent prior to the conduct of any study-specific procedures (see also Section 5.3).

To be eligible to participate in the study, patients must meet the following criteria:

1. Male or female outpatients 7 to 17 years of age, inclusive, at Visit 1
2. Patients must meet DSM-5 criteria for MDD, confirmed by K-SADS-PL
3. Patients must have a score ≥ 40 on the Children's Depression Rating Scale-Revised (CDRS-R) at Visits 1 and 2
4. Patients must have a Clinical Global Impressions-Severity (CGI-S) score ≥ 4 at Visits 1 and 2
5. Patients must have a caregiver who can and is willing to consent to be responsible for safety monitoring of the patient, provide information about the patient's condition, oversee the administration of investigational product, and accompany the patient to all study visits (see Section 5.3)
6. Patients must have normal physical examination findings, vital sign values, clinical laboratory test results, and electrocardiogram (ECG) results or abnormal results that are judged not clinically significant by the Investigator
7. Female patients of childbearing potential must have a negative serum β -human chorionic gonadotropin (β -hCG) pregnancy test result at Visit 1
8. No known active COVID-19 infection. Subject must not have signs/symptoms associated with COVID-19 infection or known exposure to a confirmed case of COVID-19 infection during 14 days prior to Screening.

